5.3 Use Phase

5.3.1 Unscheduled Study Site Visits

During any unscheduled visit to a study site for purposes of subjects obtaining additional IP, the study staff contact with the subjects will be limited to:

1. Dispensing additional IP with no questions asked or answered or directions given about the use of the IP by the study staff.
2. Appropriately documenting the IP dispensed.
3. Assisting any subject presenting self-reported AEs by immediately having the subject contact PEGUS Research.

5.3.2 Telephone Interviews

The two scheduled phone interviews will be conducted by PEGUS Research clinical staff (usually nurses) to collect information regarding AEs and concomitant medications.

During the 6 weeks of the study, subjects will be contacted by phone on Days 14 (with an allowable window of ± 3 days) and 42 (± 4 days) to answer phone interview questions and provide information on AEs and concomitant medication (and, in the end of study interview, about pregnancy test results).

In addition, several non-leading questions will be asked about behavior at the two phone interviews. Information will be asked for during both phone interviews in a masked manner to avoid influencing future behavior (e.g., “Besides taking the medication, is there anything else you have done to prevent pregnancy since we last spoke?”).

Subjects will be compensated for their time and effort to enroll and participate in the study at designated intervals during the study.

5.3.2.1 Week 2 Interview

The intent of the week 2 interview is to collect information about the initial use of the product. Because subjects in this study will be invited to participate after independently presenting to the clinic or the pharmacy seeking EC (and not in response to advertising), it is expected that most subjects will be purchasing EC for immediate use (because they have very recently had an episode of unprotected sex), rather than solely for advanced provision. The interview at 2 weeks is intended to ascertain whether the subject took the IP, and if so, to collect information about when she took ella[®] in relation to her enrollment visit (and in relation to their most recent episode of unprotected sex) and measure other behaviors in the period immediately surrounding taking the product. Timing of this interview is expected to be long enough after enrollment to allow for capturing of use within or outside of the 5-day window and resumption or starting of hormonal contraception use in the 5 or more days after ella[®] intake, but also to be soon enough that recall should not be problematic. Information about AEs and changes to concomitant medications will also be collected.

5.3.2.2 Week 6 Interview

Timing of the Week 6 interview is intended to allow for most women to have had at least one menstrual period after enrollment. Questions will be designed to collect information about behaviors related to EC use outside of the immediate period after use, as well as responses to a missed period. Information about AEs and changes to concomitant medications will also be collected.

5.3.2.3 End-of-Study Interview

In most cases, the EOS interview will take place in conjunction with the 6-week telephone call together with the week 6 interview. However, it is conceptualized as a separate interview in order to allow for collection of key end of study measures in cases where subjects elect to withdraw before the 6-week telephone call. The end-of-study interview will collect information from the subject regarding the use of other forms of contraception, including other uses of EC (if any) within the study period, and the timing of such use. Subjects will also be asked about possible pregnancy, and will be asked to report the results of their EOS pregnancy test. This interview allows for direct questions about the rationale behind any behaviors that are not consistent with the DFL and CIL, without concern about biasing the subject's subsequent behavior.

5.4 Subject Withdrawal (Early Termination)

An EOS interview will be conducted with any subject who discontinues or withdraws consent prior to Week 6, unless the subject withdraws consent for disclosure of future information. This interview will attempt to collect the EOS information and the reasons for the subject's early termination. If the subject withdraws from the study between days 1 and 17 (day 14+3), the clinical interviewer will attempt to complete the Week 2 and EOS interviews and gather EOS pregnancy test results. If the subject withdraws between days 17 and 46 (day 42+4), the clinical interviewer will attempt to complete the Week 6 and EOS interviews and gather EOS pregnancy test results. See Sections 6.4, 6.5, and 6.6 for more detailed information on the interviews.

Subject participation may be terminated by an investigator during the study for any of the following reasons:

- Significant protocol violation;
- AEs, including SAEs;
- Pregnancy;
- Physician decision;
- Subject's request;
- At the discretion of the Investigator or designee if s/he feels that study discontinuation is necessary to protect the subject, or that there are unmanageable factors that will interfere significantly with the study procedures and/or the interpretation of results.

Any such subjects will be asked to return any unused study medication and empty packaging and will be precluded from purchasing additional study medication, but earlier

collected data will be used and ongoing data collection will be allowed, unless the subject requests otherwise.

Subjects may withdraw from the trial at any time at their own request, or they may be withdrawn at any time at the discretion of the Investigator or Sponsor (or Sponsor designee) for safety or behavioral reasons, or the inability of the subject to comply with the protocol required schedule of study visits or procedures at a given study site.

If a subject refuses contact for scheduled follow-up calls, any efforts made to contact the subject will be documented. In any circumstance, every effort will be made to document subject outcome, if possible. The investigator will inquire about the reason for withdrawal, request the subject to return all unused IP(s) and empty packaging, request the subject to participate in a final telephone interview, if applicable, and follow up with the subject regarding any unresolved adverse events (AEs).

If the subject withdraws from the study, and also withdraws consent for disclosure of future information, no further evaluations will be performed, and no additional data will be collected. The Sponsor may retain and continue to use any data collected before such withdrawal of consent.

[figure not shown]
A subject may be declared lost to follow-up if, during the study, the available contact information is determined to be incorrect and no other information is available. Every attempt will be made to contact lost to follow-up subjects, including three phone call attempts and a United States Postal Service (USPS) letter. Subjects whose status is withdrawn, lost to follow-up, withdrawal due to an AE or withdrawal from the study for other reasons will be recorded in the case report form (CRF).

If a subject wishes to discontinue his or her participation in the study, the Investigator/interviewer will document the reason for withdrawal, ask the EOS questions where possible and follow-up with the subject regarding any new or unresolved AEs and collect or make arrangements to collect all IP provided to the subject. Data collected up to the point of withdrawal will be retained and used as appropriate in the data analysis.

5.5 Study Flow

Study procedures are represented in a flow chart in Figure 1 below.

Figure 1 Study Procedures Flowchart

6 ASSESSMENTS

Every effort will be made to ensure that the protocol-required tests and procedures are completed as described. However, it is anticipated that from time to time, there may be circumstances outside of the control of the Investigator that may make it unfeasible to perform the test. In these cases, the Investigator will take all steps necessary to ensure the safety and well-being of the subject. When a protocol required test cannot be performed, the Investigator will document the reason for this and any corrective and preventive actions which he/she has taken to ensure that normal processes are adhered to as soon as possible.

The study team will be informed of these incidents in a timely fashion. All data will be collected using an Electronic Data Capture Data Collection Instrument (DCI).

6.1 Screening Assessment

Subjects will be screened during the initial visit to determine those individuals who will be included or excluded from the trial.

6.2 Enrollment Interview

Subjects will be shown the ella® outer package and allowed to make a decision about whether the product is appropriate for them to use, and whether to purchase ella® for their own use. Subsequent questions will be asked to gather limited medical and medication history as it pertains to use of the product.

6.3 Reading Level Assessment

The REALM¹ (for adults) or the REALM-Teen² (for adolescents) test will be used to measure reading grade level and will be the measure of literacy used for this study. The REALM score corresponds to four grade-equivalent reading levels as shown in Table 2 below, while the REALM-Teen score corresponds to 5 grade-equivalent reading levels as shown in Table 3 below. A REALM score of 60 or less (a reading level of 8th grade or lower) defines the low literacy subgroup among adult subjects.

The REALM-Teen test does not have a 9th grade reading level cutoff, so a cutoff score of 60 or lower will be used to define the low literacy cohort for the adolescent group as well (which is the midpoint of the 8th - 9th grade-equivalent reading level). This allows for a somewhat more conservative requirement to be classified as low literacy among the adolescent cohort in comparison to the cutoff for 10th grade-equivalent reading level.

The REALM-Teen will be used to demonstrate (along with demographics) that adolescent subjects represent a diversity of age, race, educational attainment, and reading ability. However, given the relatively small absolute number of low literacy adolescents expected (if 25% of the sample of 175 adolescents meet the criteria, this would yield approximately 44 low-literacy adolescents), low literacy adolescents will be included with low literacy adult subjects to comprise the overall low literacy subgroup.

Table 2 REALM Test Grade-Equivalent Reading Levels

REALM ¹ Score	Grade-equivalent Reading Level	Included as Low-literacy	Included as Normal-literacy
0-18	3 rd	X	
19-44	4 th to 6 th	X	
45-60	7 th to 8 th	X	
61-66	9 th and above		X

Table 3 REALM-Teen Test Grade-Equivalent Reading Levels

REALM-Teen ² Score	Grade-equivalent Reading Level	Included as Low-literacy	Included as Normal-literacy
0-37	3rd	X	
38-47	4th - 5th	X	
48-58	6th - 7th	X	
59-62	8th - 9th	≤ 60	≥ 61
63-66	10th and above		X

Given that literacy (as measured by the REALM or REALM-Teen) is not known in advance and cannot be directly used in screening in an actual use trial, recruitment targets for low literacy are not set. In self-selection and actual use studies that recruit in the typical manner, the proportion of low literacy subjects typically ranges from 12-18%. In contrast with label comprehension studies, whose samples are meant to be approximately representative of the general population and therefore controlling for factors of interest like literacy is potentially justified, one of the overarching goals of an actual use trial is to enroll a sample based on individuals who present seeking the product, and this approximates the likely OTC user population. Actual use trials seek to enroll subjects who seek out the product as they are those most likely to use the product when available OTC. In this case, forcing a certain percentage of low-literacy enrollment would compromise the representativeness of the sample in a manner that is inappropriate. While it is inappropriate to force a specified proportion of low literacy subjects in an AUT, it is still important to have a sample of low literacy participants of sufficient size to allow for conclusions to be drawn as to performance of study endpoints among subjects of low literacy. The total sample size of this study was selected to ensure that the absolute size of the subgroup of low literacy participants will be large enough to evaluate the endpoints among those of low literacy. If 15% of 950 subjects are classified as low literacy by the REALM or REALM-Teen, the cohort of low literacy subjects will be approximately 143 subjects, representing a low literary subgroup of sufficient size. As an illustration, the 95% confidence interval (exact) around a point estimate of 85% for 143 subjects is +/-7%.

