3.2 Study Sites

Approximately 25 women's health clinics and 10 retail pharmacies will be chosen for this study as they provide an environment that is considered typical of those from which consumers may expect to find this product following approval, and which represent the places women currently go to seek EC in an OTC-like setting. The women's health clinics sell currently available OTC EC in an OTC-like manner without the requirement to see a clinician. These clinics typically have a window or a front desk area where women purchase EC by requesting it from non-clinical staff, in a manner similar to consumers purchasing an OTC product in a pharmacy.

Study sites will be selected to provide geographic and demographic diversity. They will be selected from approximately eight geographic regions in the US. Each site has a private office or a suitable semi-private area where the study will be carried out privately and without distraction. The study area will also have all of the necessary computer equipment and a high-speed Internet connection to accommodate the electronic data capture system (EDC).

It is expected that subjects enrolled through health centers are likely to be younger on average and have higher prevalence of low literacy than subjects who might respond to recruitment for a more typical AUT.

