9.1 Sample Size Determination

For the purposes of this AUT, sample size has been set for practical and logistical reasons at approximately 950 purchasers. Given that subjects are recruited after independently seeking EC, most of those who enter the self-selection phase are expected to purchase, and most purchasers are expected to actually use the product during the study. If approximately 75% of subjects pass the screening criteria, self-select

and both qualify and agree to purchase and enter the use phase, it is expected that up to 1270 subjects will need to be interviewed to yield 950 purchasers.

Assuming approximately 950 purchasers, if 80% of those purchasers use the product within the study period, that would yield a user population of 760. Estimating approximately 40% of users will have had recent hormonal contraceptive use would yield a recent hormonal contraceptive users population of 305. Allowing for a further 20% loss to follow-up yields a user population of approximately 608 and a recent hormonal contraceptive user population of 245.

Because actual use trials are not hypothesis-testing comparative trials, study sample size is designed to allow for adequate evaluation of key endpoints across all subjects and among several subgroups. As the analysis of actual use trials typically focuses on estimating the proportion (and associated 95% confidence intervals) of individual endpoints, sample size is most often based on the number of subjects needed to constrain the confidence interval (CI) to a limited range. For this study, assuming 85% correct response (the confidence interval depends on the actual point estimate), a sample of 608 subjects would constrain the CI to $\pm 3.1\%$. For purposes of illustration, Table 5 provides the 2-sided exact 95% confidence interval for various sample sizes around a point estimate of 85%.

Table 5 Two-sided 95% CIs for Various Sample Sizes Around 85% Point Estimate

	N=760 ^a	N=608 ^b	N=245 ^c	N=143 ^d
95% CI around a point estimate of 85%	$\pm 2.7\%$	$\pm 3.1\%$	$\pm 5.1\%$	$\pm 7.0\%$

^a User population (maximum)

^b User population (allowing for loss-to-follow up)

^c Recent hormonal contraceptive users

^d Low literacy subjects

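### The low-literacy N of 143 counts purchasers but is offered as adequate for endpoints measured in users, and the evaluable-user N is itself stated two ways

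*Protocol*

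**What the plan says.** Section 6.3 sets no recruitment target for low literacy. It relies on total sample size instead, which it says was chosen so that the subgroup would be "large enough to evaluate the endpoints among those of low literacy". Taking 15% of 950, it concludes that "the cohort of low literacy subjects will be approximately 143 subjects, representing a low literary subgroup of sufficient size", and illustrates this with an exact 95% interval of ±7% around 85%. For the share it says: "In self-selection and actual use studies that recruit in the typical manner, the proportion of low literacy subjects typically ranges from 12-18" percent. Section 3.2 adds that subjects from health centers "are likely to be younger on average and have higher prevalence of low literacy" than in a more typical actual use trial, without giving a figure.

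Section 9.1 identifies the 950 as purchasers. It continues: "if 80% of those purchasers use the product within the study period, that would yield a user population of 760". Then: "Allowing for a further 20% loss to follow-up yields a user population of approximately 608". Table 5 gives ±2.7% for N=760, ±3.1% for N=608, ±5.1% for N=245 and ±7.0% for N=143. Its footnotes label the first three as users or recent hormonal contraceptive users (608 as "User population (allowing for loss-to-follow up"). The fourth is labelled only as low-literacy subjects.

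The Protocol Summary (Number of Subjects) applies the 80% to purchasers who both use the product and take part in at least one follow-up call, and gives 760 as the population for evaluating the primary endpoints.

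**The concern.** Subjects who buy the product but never take it contribute nothing to A, B or F, which count dosing instances, or to H, which counts users. In Table 5 the first three columns carry the 80% use rate, and 608 and 245 also carry the 20% loss to follow-up. The low-literacy column carries neither, and a reader of the table cannot see that.

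This bears on the only support given for the subgroup's size. Section 9.3 commits to presenting endpoints by literacy and to by-subject analyses of the dosing-instance endpoints. The size and precision offered for that purpose hold for purchasers, not for the users in whom A and B are observed.

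Separately, the same 80% means use plus a call in the Summary and use alone in section 9.1. That leaves open which user base applies, both overall and for this subgroup.

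**Working it through.** **Inputs.** 950 purchasers, 80% use and a further 20% loss (9.1). 15% low literacy and the 12–18% range (6.3). Two-sided exact 95% interval at 85% (6.3, Table 5). Endpoint denominators (9.3.1 and 9.3.3).

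**The plan's figures reproduced**
- 0.15 × 950 = 142.5, rounded to 143.
- Clopper-Pearson interval with x = 0.85N: lower limit = Beta(0.025; x, N−x+1), upper limit = Beta(0.975; x+1, N−x).
- The interval is asymmetric, and the printed ± is the lower-side distance: 2.74 for N=760, 3.09 for 608, 5.10 for 245 and 6.93 for 143 (6.98 at 121/143). The printed values are 2.7, 3.1, 5.1 and 7.0.

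The arithmetic for 143 is therefore right for purchasers.

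**User base**
- 950 × 0.80 = 760, and 760 × 0.80 = 608. The two statements of the evaluable-user N differ by 152 subjects.
- 0.15 × 760 = 114, and 0.15 × 608 = 91.2, about 91.

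| Base at 15% | N | Lower distance (points) | Upper distance (points) |
|---|---|---|---|
| Purchasers (950) | 143 | 6.9 | 5.4 |
| Users (760) | 114 | 7.9 | 6.0 |
| Users after loss (608) | 91 | 9.0 | 6.6 |

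**Range of the share, 12–18%**
- Of 760: 91 to 137 users, lower distance 9.0 to 7.1 points.
- Of 608: 73 to 109 users, lower distance 10.3 to 8.1 points.
- Share needed for 143 users: 143/760 = 18.8%, or 143/608 = 23.5%.

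**Repeat doses.** A, B and F count dosing instances, so their N can exceed the number of users. Reaching 143 would take 143/114 = 1.25 or 143/91 = 1.57 doses per user. Section 4.3.2 expects nearly all subjects to buy one package and very few to return. Repeat doses do not help H or the by-subject analyses.

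**Other endpoints**
- C and D use female selectors and E uses the self-selection population. Section 9.1 says "it is expected that up to 1270 subjects will need to be interviewed to yield 950 purchasers", and 0.15 × 1270 = 190.5. That is an upper figure because it includes screen failures. So 143 is not shown to be too high for these three.
- G uses only instances followed by starting or restarting hormonal contraception in the same cycle. The protocol gives no share for it.
- I uses only takers of the listed products.

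**The case against.** The strongest reply is that the base is disclosed: section 6.3 names 950, section 9.1 calls them purchasers, and nowhere does the protocol claim 143 low-literacy users. That is true, but 6.3 ties 143 to the endpoints without limiting which, and Table 5 puts it in a row of user counts.

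A second reply is that the figures are illustrations, with no subgroup target, precision criterion or success rule. This stands as to consequences: nothing in the protocol makes 114 or 91 insufficient. It does not rescue the text, because the illustration is the interval, while the sufficiency statement is a conclusion resting on 143.

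Third, section 6.3 also supposes that 25% of the 175 adolescents, about 44, have low literacy, and pools them into this subgroup. With 15% of 775 adults (116) that gives 160 purchasers, hence 160 × 0.80 = 128 users (lower distance 7.4 points) or 160 × 0.64 = 102 (8.4). With 18% of adults it gives 147 (6.8) or 117 (7.8). So on the 760 base a higher share could remove the shortfall. This is a fair limit on the size of the effect. However, the flat 15% is the protocol's own choice for 143, and with 15% of adults the mixed share still falls short of 143 on either user base.

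Finally, 760 is labelled a maximum in Table 5, and both precisions are printed. The Summary nevertheless gives 760 as the number evaluable after follow-up, which section 9.1 does not.

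**Conclusion.** The concern holds. For H and the by-subject analyses of A, B and F, the low-literacy base at a 15% share is about 114 or 91 users, not 143. The lower interval distance at 85% is 7.9 or 9.0 points against the printed 7.0. Repeat doses could narrow this slightly for A, B and F counted by dosing instance.

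These figures assume that low-literacy purchasers use the product and stay in follow-up at the overall rates. The 12–18% range is an assumption, not a ceiling. The 760/608 conflict is a separate fault, worth ±2.7 or ±3.1 points overall.

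The effect is modest, and no subgroup success rule, analysis or subject number depends on it. It should still be corrected, because the protocol rests the adequacy of this subgroup on the figure.

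**What to change.** 1. State one evaluable-user N in the Protocol Summary and section 9.1, and say whether the 80% covers use alone or use plus at least one call.
2. In section 6.3 and Table 5, label 143 as low-literacy purchasers. Add the low-literacy user N and exact interval for A, B, F and H on the chosen base: about 114 (lower distance 7.9 points) on 760, or about 91 (9.0) on 608, at 15%.
3. State the assumption of equal use and follow-up by literacy, and note that A, B and F count dosing instances. Show 12–18% as a range (91–137 or 73–109), and say whether the 25% adolescent share is included.
4. Note that G rests on a smaller subset, and that C and D, E, and I each have their own base. Tie the sufficiency statement to the base it refers to.

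The cost is text and one table column. No subjects are added, and no decision rule or analysis changes. The stated low-literacy precision for A, B, F and H becomes about 1 to 2 points less favourable at a 15% share.
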